1.1 Synopsis

Name of Sponsor: Otsuka Pharmaceutical Development & Commercialization, Inc.

Name of Investigational Digital Therapeutic: CT-152

Protocol No.: 345-201-00002

Protocol Title: A Multi-center, Randomized, Controlled Trial to Evaluate the Effectiveness of a Digital Therapeutic (CT-152) as Adjunctive Therapy in Adult Subjects Diagnosed with Major Depressive Disorder (MDD)

Protocol Lay Person Short Title: Trial to Evaluate the Effectiveness of a Digital Therapeutic (CT-152) as Adjunctive Therapy in Adult Subjects Diagnosed with MDD

[figure not shown]
Clinical Phase/Trial Type: Pivotal trial

Treatment/Indication: Major depressive disorder in adults

Objectives and Endpoints:

The objectives and endpoints are provided in table below.

Objectives Endpoints Primary objective: To compare the effectiveness Primary efficacy endpoint: Change from baseline to Week 6 in the MADRS total of CT-152 with sham, in adult subjects diagnosed with MDD who are on ADT score. monotherapy. The durability of effect will include 3 MADRS assessments at Weeks 6, 8, and 10.**CC** Key secondary efficacy endpoint: Change from baseline to Week 6 in the GAD-7 total score. Durability based on GAD-7 will include 3 assessments, at Weeks 6, 8, and 10, demonstrating a numerically larger improvement on point estimate of the difference in the change from baseline in GAD-7 total score at Weeks 8 and 10 in CT-152 compared to sham. Other efficacy endpoints: Change from baseline to Weeks 2 and 4 in the MADRS total score Change from baseline to Weeks 2 and 4 in the GAD-7 total score MADRS response rate ($\geq 50\%$ reduction from baseline) at Weeks 2, 4, and 6. Change from baseline to Weeks 2, 4, and 6 in the CGI-S score. Change from baseline to Week 6 in the WHODAS 2.0 total score. Change from screening to Weeks 4 and 6 in the PHQ-9 total score. MADRS partial response (MADRS score reduction from baseline $\geq 30\%$ and < 50%) at Weeks 2, 4, and 6. MADRS response rate (full or partial, defined as \geq 30% reduction in MADRS total score from baseline) at Weeks 8 and 10.

Note: The sham is a control that deploys only a working memory exercise.

AE = adverse event; ADT = antidepressant therapy; CGI-S = Clinical Global Impressions-Severity;

; GAD-7 = Generalized Anxiety Disorder-7; MADRS = Montgomery-Asberg Depression Rating Scale;

; PHQ-9 = Patient Health Questionnaire-9;

WHODAS = World Health Organization Disability Assessment Schedule.

Trial Design:

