9.1 Sample Size

The initial sample size is calculated to detect a 3-unit difference between CT-152+ADT and sham+ADT in the change from baseline in MADRS total score with 85% power at a 2-sided $\alpha = 0.05$ level, assuming a common standard deviation of 9. The resulting sample size is 324 evaluable subjects in total (162 subjects in each arm). To compensate for subjects that fail to have evaluable assessments of MADRS total score in the full analysis set (FAS) sample (estimated at up to 10% of all subjects), a total of 360 subjects (180 subjects in each arm) will be randomized in this trial.

Due to the limitations of applying assumptions on the treatment effect size, and in order to ensure adequate power of the trial, an unblinded interim analysis will be conducted by a Data Monitoring Committee (DMC; see Section 9.5.1). The final sample size could be increased to 540 subjects (270 subjects in each arm) as per recommendation of the DMC. Using the O'Brien-Fleming spending function⁴⁹ a significance level of 0.003 (2-sided) is allocated to this interim analysis. The corresponding final significance level is 0.049 (2-sided).

The trial will randomize eligible subjects 1:1 across approximately 50 trial sites. The sample size at any single trial site will be capped at approximately 15% of the total number of randomized subjects. Randomization will be stratified by trial site.

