In this hypothetical strategy, the event of withdrawing CT-152+ADT or sham+ADT is considered missing at random (MAR), and the primary endpoint of the trial could be considered as a combination of the measurements of on-treatment completers at Week 6 and the imputation of the endpoint to Week 6 following the trend in each treatment group using the mixed model repeated measurements (MMRM) method to impute missing data for subjects who withdraw CT-152+ADT or sham+ADT during the trial. All data collected during the trial treatment period will be used for statistical analysis. For the primary efficacy analysis, the treatment effect will be estimated using the MMRM method described in Section 9.4.1.1.2. Under the MAR assumption, MMRM provides an unbiased estimate of treatment effect for the treatment period. Analyses with missing values imputed by multiple imputation under missing not at random (MNAR), and other methods will be performed as sensitivity analyses.

Protocol No. 345-201-00002

9.4.1.1.2 **Primary Analysis Method**

The primary analysis will utilize a MMRM with treatment, visit, treatment by visit interaction, and site as fixed effects to assess heterogeneity of treatment effects. This model will also include an interaction term of visit by baseline MADRS total score as a covariate. Observed data from all planned visits during the 6-week treatment period will be included in the model. An unstructured covariance matrix will be used to model the within subject variance. The primary comparison between the CT-152+ADT or sham+ADT at Week 6 will be estimated as the difference between least squares means utilizing the computing software SAS procedure PROC MIXED.

The mathematical formula for the MMRM model is as follows:

$$y = X\beta + Zu + \epsilon$$

Where

y denotes the observed vector of change from baseline to Week 6 in MADRS total score;

X is the known matrix for the fixed effects and covariate;

 β is an unknown fixed-effect parameter vector;

Z is the known matrix for the random effect of subject;

u is an unknown vector of random effect of subject with mean 0 and variance-covariance matrix **G** (unstructured covariance matrix);

 ϵ is an unknown vector of random errors with mean 0 and variance **R**.

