9.4.1.2.3 Other Efficacy Endpoints Analyses

Change from baseline to Weeks 2 and 4, separately, in the MADRS total score will be analyzed using the same MMRM model in the primary efficacy analysis.

Change from baseline to Weeks 2 and 4, separately, in the GAD-7 total score will be analyzed using the same MMRM model in the key secondary efficacy analysis.

Response on the MADRS is defined as a decrease of 50% or more on the MADRS total score from baseline. Response rates at Weeks 2, 4, and 6, separately, will be analyzed using the Cochran-Mantel-Haenszel General Association Test controlling, in last observation carried forward (LOCF) analyses, for trial site.

$$H_0$$
: $\pi_{CT-152+ADT} = \pi_{sham+ADT}$

$$H_A$$
: $\pi_{CT-152+ADT} \neq \pi_{sham+ADT}$

Where $\pi_{\text{CT-152+ADT}}$ and π_{sham} are the proportion of MADRS response rates at Weeks 2, 4, and 6 in CT-152+ADT and sham+ADT treatment groups, separately.

Change from baseline to Weeks 2, 4, and 6, separately, in CGI-S score will be analyzed using the same method as in the primary analysis with a replacement of the interaction term of visit by baseline CGI-S score as a covariate. The hypothesis tested is the null hypothesis that the change from baseline to each schedule week (Weeks 2, 4, and 6) in the CGI-S score using CT-152+ADT is equal to the change from baseline to each schedule week (Weeks 2, 4, and 6) in the CGI-S score using the sham+ADT.

$$H_0$$
: $\Delta \mu_{\text{CGI-S CT-152+ADT}} = \Delta \mu_{\text{CGI-S sham+ADT}}$

$$H_A$$
: $\Delta \mu_{CGI-S CT-152+ADT} \neq \Delta \mu_{CGI-S sham+ADT}$

75

Protocol No. 345-201-00002

Where $\Delta\mu_{\text{CGI-S CT-152+ADT}}$ and $\Delta\mu_{\text{CGI-S sham+ADT}}$ are the changes from baseline to Weeks 2, 4, and 6 in CGI-S score in CT-152+ADT and sham+ADT treatment groups, separately.

Change from baseline to Week 6 in the WHODAS 2.0 total score will be evaluated using the analysis of covariance with baseline as a covariate and treatment and, in LOCF analyses, trial site as main effects. The hypothesis tested is the null hypothesis that the change from baseline to Week 6 in the WHODAS 2.0 total score using CT-152+ADT is equal to the change from baseline to Week 6 in the WHODAS 2.0 total score using the sham+ADT.

 H_0 : $\Delta \mu_{WHODAS\ 2.0\ CT-152+ADT} = \Delta \mu_{WHODAS\ 2.0\ sham+ADT}$

 H_A : $\Delta\mu$ whodas 2.0 ct-152+adt $\neq \Delta\mu$ whodas 2.0 sham+adt

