# 4 Sample Size and Power Justification

The primary efficacy endpoint is the change from baseline at Week6 in Montgomery-Asberg Depression Rating Scale (MADRS) total Score. The trial will compare CT-152 to sham, randomized at a ratio of 1:1, with an overall alpha of 0.05 for the primary efficacy endpoint.

The initial sample size is calculated to detect a 3-point difference between CT-152+ADT and sham+ADT in the change from baseline in MADRS total score with 85% power at a 2-sided  $\alpha$  = 0.05 level, assuming a common standard deviation of 9. The resulting sample size is 324 evaluable subjects in total (162 subjects in each arm). To compensate for subjects that fail to have evaluable assessments of MADRS total score in the full analysis set (FAS) Sample (estimated at up to 10% of all subjects), a total of 360 subjects (180 subjects in each arm) will be randomized in this trial.

Due to the limitations of applying assumptions on the treatment effect size, and in order to ensure adequate power of the trial, an unblinded interim analysis (IA) will be conducted by a Data Monitoring Committee (DMC) on when approximately the first 180 randomized subjects had an opportunity to complete the Week 6 visit. The final sample size could be increased to 540 subjects (270 subjects in each arm) as per recommendation of the DMC. Using the O'Brien-Fleming spending function, an alpha level of 0.003 (2-sided) is allocated to this interim analysis. The alpha level left for the final analysis is 0.049 (2-sided). The power and sample size were obtained using the PASS 14 (2015) statistical computing software.

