The last-observation-carried-forward (LOCF) data set will include data recorded at a scheduled visit during or, if no observation is recorded at that visit, data carried forward from the previous scheduled visit. For the treatment period, baseline data will not be carried forward to impute missing values. For the extension period, the only imputation will be applied to Week 10 data. If no observation is recorded at Week10, available observations from Week 8 will be carried forward. Week 6 data will not be carried forward to impute missing values at Week 8. The analysis of covariance (ANCOVA) analysis will be primarily performed on the LOCF data. The model will include treatment and study center as main effects, and baseline value as a covariate. The ANCOVA analysis will also be applied on the OC dataset, where study center will not be included in the model.

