# 3 Supportive Analyses for the Primary Efficacy Endpoint

The following endpoints from Section 8.3 (Other Efficacy Endpoints) CCl

in the original SAP will be served as supporting evidence to the primary efficacy endpoint:

- 1) Change from baseline to Weeks 2 and 4 in the MADRS total score
- 2) MADRS full response at Weeks 2, 4, and 6
- 3) MADRS partial response at Weeks 2, 4, and 6
- 4) MADRS remission at Weeks 2, 4, and 6

Confidential - Proprietary Information

SAP 345-201-00002

Note that in order to differentiate with MADRS partial response, MADRS response in the original SAP is renamed as MADRS full response.

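### WHODAS 2.0 and MADRS response lean on LOCF, which is inconsistent with the primary analysis's missing-data assumption and can move the response difference either way

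*Protocol*

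**What the plan says.** **Role of LOCF.** The Protocol Synopsis (1.1) lists "Change from baseline to Week 6 in the WHODAS 2.0 total score" among the other efficacy endpoints, beside MADRS response and partial response. Protocol 9.4.1.2.3 tests MADRS response with the "Cochran-Mantel-Haenszel General Association Test controlling, in last observation carried forward (LOCF) analyses, for trial site". Partial response uses the same model. WHODAS is analysed by ANCOVA, again with site only in the LOCF version. SAP 5.2 ranks the data sets for ANCOVA: "The analysis of covariance (ANCOVA) analysis will be primarily performed on the LOCF data". SAP 8.3 adds observed-case (OC) analyses of WHODAS, response and partial response without site, and does not rank LOCF and OC for response.

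**What can be carried.** SAP 5.2 bars carrying baseline forward in the treatment period. WHODAS is scheduled only at baseline and Week 6 (Protocol Table 1.3-1, SAP 10.3.5). Subjects who stop before Week 6 have the Day 42 procedures at an early-termination visit, and SAP 10.1 assigns those values to a visit by study day. The Week 2 window opens on Day 2.

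**Primary analysis.** Protocol 9.4.1.1.1 and SAP 8.1.1.1 treat withdrawal as missing at random, with "the imputation of the endpoint to Week 6 following the trend in each treatment group" through the MMRM. Protocol 9.4.1.2 says the remaining efficacy endpoints are analysed on the FAS in the way described for the primary analysis. No estimand is stated for WHODAS or response.

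**Role of the results.** SAP Addendum section 3 says that a list of MADRS endpoints, including full and partial response, "will be served as supporting evidence to the primary efficacy endpoint". SAP 8.3 and Addendum section 2 test these endpoints and WHODAS at a nominal 0.05.

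**The concern.** The response analysis and the primary analysis use the same MADRS ratings but fill the gaps differently. The MMRM lets a dropout continue along the arm's trajectory, while LOCF stops the dropout at the last rating. If patients are still improving, LOCF lowers the response rate in both arms. The difference between arms then moves by an amount that depends on how many leave each arm, when they leave, and how much improvement they forgo. A response result could look weaker or stronger than the primary result partly because of dropout, and the Addendum asks readers to use it as support.

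For WHODAS, the LOCF data set combines Week 6 scores and early-termination scores and leaves out dropouts who have neither. The planned MNAR and multiple-imputation analyses are written for the MADRS total score. Neither response nor WHODAS therefore has an analysis in line with the primary assumption.

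**Working it through.** **1. The plan's own figure.** Protocol 9.1 sizes the trial to "detect a 3-unit difference between CT-152+ADT and sham+ADT" with SD 9, 85% power and two-sided α = 0.05. n per arm = 2 × (1.960 + 1.036)² × 9² / 3² = 161.6, so 162. The total is 324, and 324 / 0.90 = 360. This reproduces. The 10% is the share without evaluable MADRS data, not a Week 6 dropout rate. The documents give no dropout rate by arm and no expected response rate.

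**2. What LOCF can do at each visit.**
- *MADRS, Week 2:* this is the first post-baseline window and baseline is not carried, so LOCF and OC data are identical.
- *MADRS, Weeks 4 and 6:* an earlier scheduled or early-termination rating is carried.
- *WHODAS, Week 6:* only an early-termination score from before Day 35 can be carried. One taken on Days 35 to 48 is a Week 6 value in its own right. With no such score there is no value.

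**3. Closed form for response at Week 6.** Let d be the share carried forward and g the gain in response rate between the carried visit and Week 6 (T = CT-152, S = sham). If leaving is unrelated to outcome, the shift in the difference is dS × gS − dT × gT. Assumed response rates: 45% and 35% at Week 6, 15% and 12% at the carried visit. Then gT = 30, gS = 23, and the full-follow-up difference is 10 points.

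| Carried, CT-152 / sham | Shift (points) | LOCF difference |
|---|---|---|
| 10% / 10% | 2.3 − 3.0 = −0.7 | 9.3 |
| 10% / 20% | 4.6 − 3.0 = +1.6 | 11.6 |
| 20% / 10% | 2.3 − 6.0 = −3.7 | 6.3 |

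With no true effect (35% and 12% in both arms), 10% / 20% gives 4.6 − 2.3 = +2.3 points. With gains of 30 and 20 points, 10% / 15% gives 3.0 − 3.0 = 0.

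**4. Simulation with dropout depending on the last observed score.** The Week 6 difference of 3 and SD of 9 are the protocol's. The rest is assumed: baseline 30 (SD 5); mean change at Weeks 2/4/6 of −6/−10/−13 on CT-152 and −5/−8/−10 on sham; SD 7/8/9; correlation 0.6 between adjacent visits; dropout after Week 2 and after Week 4; 400,000 subjects per arm. Response is a reduction of at least 50%.

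| Dropout, CT-152 / sham | True difference | LOCF |
|---|---|---|
| 20% / 20% | 11.9 | about 10.4 |
| 20% / 10% | 11.9 | about 8.7 |
| 10% / 20% | 11.9 | about 12.7 |
| 20% / 10%, no effect | 0 | about −1.7 |
| 25% / 10%, no effect | 0 | about −2.5 |

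Repeat runs with different dropout slopes agree to within 0.3 points. In one of them the two no-effect cases gave OC differences of +1.1 and +1.5, opposite in sign to LOCF.

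**5. Scale.** With 162 per arm and assumed response rates of 45% and 35%, the standard error is √[(0.45 × 0.55 + 0.35 × 0.65) / 162] = 5.4 points. With 30% in both arms it is √[(2 × 0.30 × 0.70) / 162] = 5.1 points. The no-effect shifts are therefore about 1.7 / 5.4 = 0.3 to 2.5 / 5.1 = 0.5 standard errors.

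**The case against.** The strongest reply is that little depends on these analyses. Response and WHODAS are tested at a nominal level outside type I error control. Trial success rests on the primary MMRM, which has delta-adjusted, sham-based and other MNAR analyses behind it. That stands, and it limits the weight of the point.

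The size can also be questioned. The no-effect shifts are below half a standard error and, with more dropout on CT-152, run against CT-152. The simulation carries only Week 2 and Week 4 scores. Adding an early-termination rating midway reduced the 20% / 10% shift from about −3.2 to −2.6 points. All dropout rates and visit means are assumed. These limits stand too, but the shift does not disappear.

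The planned OC analysis does not settle the matter. It drops the dropouts, leaves out site, and in the no-effect cases erred in the opposite direction from LOCF.

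Some stronger readings are tempting, but the documents do not support them:
- *That LOCF contradicts the primary analysis.* The trend assumption belongs to the primary estimand, and none is set for these endpoints. This is an inconsistency of assumptions, sharpened by the general statement in Protocol 9.4.1.2.
- *That LOCF is declared the main analysis of response.* The ranking sentence in SAP 5.2 covers ANCOVA only. For response it is an inference from where site is controlled.
- *That WHODAS supports the primary endpoint.* Addendum section 3 lists MADRS endpoints only, and one of them, change at Weeks 2 and 4, uses the primary MMRM.

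**Conclusion.** The point holds as a recommended improvement. LOCF leads for WHODAS and, by implication, for MADRS response and partial response. Its assumption differs from that of the primary analysis of the same ratings, and response has since been given a supporting role.

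Under the assumed inputs, LOCF moves a true response difference of 11.9 points by about −3.2 to +0.8 points (8.7 to 12.7), and a true difference of zero by about −1.7 to −2.5 points. The direction depends on dropout and on improvement in each arm. A reader might infer that any imbalance in dropout shifts the result, or that balance protects it. Neither follows: the closed form gives no shift at 10% / 15% with gains of 30 and 20 points, and the simulation gives about −1.5 points at 20% / 20%.

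Week 2 response is untouched by LOCF. No size can be given for WHODAS, because the documents provide neither its expected scores nor the share of dropouts with an early-termination score. Nothing here affects the primary conclusion.

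**What to change.** In SAP 8.3 and Protocol 9.4.1.2.3, make multiple imputation under missing at random, on the FAS, the main analysis of these endpoints.

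- **MADRS response and partial response.** Impute MADRS totals with treatment arm in the model, or separately by arm, following the PROC MI steps of SAP 8.1.3. State both choices: the SAP does not say its imputation is by arm, and it sets 100 imputations only for the Randomized Sample analysis in 8.1.3.4. Derive the categories at Weeks 4 and 6, and at Week 2 where missing. Estimate the site-stratified difference in each data set and combine with PROC MIANALYZE.
- **WHODAS.** Impute Week 6 from baseline WHODAS and the MADRS and GAD-7 visits, then fit the ANCOVA with baseline and site. This imputation model is new to the SAP.
- **LOCF and OC.** Keep both as sensitivity analyses.

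The cost is SAP and protocol wording and modest programming. No new data are needed. Standard errors will be slightly larger, because the uncertainty of the imputed values is then counted.

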Sham will provide a cognitive training exercise designed to retain user interest while minimizing any therapeutic effect. Each treatment session will consist of a Shapes

Memory Task (SMT) exercise. It will present users with an analogous structure, matched for time and attention to the cognitive-emotional training exercise found in CT-152. In order to retain the intended placebo nature of the sham, it will not include EFMT or psychotherapy content.

Subjects will participate in the trial for up to 13 weeks. This includes a screening period of up to 3 weeks; due to the onboarding adherence requirement, a minimum of 7 consecutive days will be required for screening. Extensions to the screening period, if requested by the investigator, may be granted after discussion and approval by the medical monitor.

The intervention will begin the same day as the baseline visit, once the baseline visit has been completed. The subjects will progress through a treatment schedule of 18 sessions (approximately 30 - 45 minutes) at a rate of 3 sessions per week over the 6-week treatment period (Day 1 [baseline] to Week 6).

After Week 6, subjects will continue participation in the trial during the extension period (Weeks 7 to 10). In the extension period, the digital mobile applications will remain installed for each group with EFMT and SMT no longer available. Psychotherapy content provided previously will remain available for optional reference in the CT-152 group but no new therapeutic content will be introduced and no required treatment schedule is in place. The 2 groups will each receive brief SMS messages in the extension period reminding subjects of the previously completed CT-152 and sham treatment courses.

A dedicated call center is available to support the subject and the trial site on the initial downloading of and access to the digital mobile application, as well as any technical issues with the digital mobile application throughout the trial.

Subjects must be instructed by the investigator to contact the call center with any technical questions about the digital mobile application. All calls to the call center will be documented and processed. Basic user technical issues will be resolved by the call center.

If a subject contacts the call center with an AE, the call center will log the call and will immediately provide this information to the trial site and sponsor or sponsor's designee for follow-up.

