- The baseline MADRS must be completed prior to or on the day of the baseline visit, or prior to usage of the digital therapeutic treatment following randomization. The MADRS is conducted by the blinded and independent rater and should be scheduled by the trial site staff.
- The following will be administered by the trial site staff: CGI-S and C-SSRS.
- The following will be completed by the subject: GAD-7 and WHODAS 2.0.
- Prior/concomitant therapy and AEs will be recorded.

Treatment Period

The following will be performed during the remote visits at Weeks 2, 4, and 6:

- Check of ADT compliance.
- Adherence check of the use of the digital mobile application (Weeks 2 and 4 only).
- The MADRS will be conducted by the blinded and independent rater. Except for the baseline MADRS (see above), the MADRS at other visits may occur separately from the remote trial site visit but must be performed within the window.
- The following will be administered by the trial site staff: CGI-S and C-SSRS.

Protocol No. 345-201-00002

- The following will be completed by the subject: GAD-7, WHODAS 2.0 (Week 6 only), PHQ-9 (Weeks 4 and 6 only), CCl and CCl
- The principal investigator or the clinical trial member most familiar with the subject will complete the CCl
- Concomitant medications and AEs will be recorded.

During each telephone contact by the trial site at Weeks 1, 3 and 5, concomitant medications and AEs will be recorded and an adherence check of the use of the digital mobile application will be performed.

Extension Period

The following will be performed during the remote visits at Weeks 8 and 10:

- Check of ADT compliance.
- The MADRS will be conducted by the blinded and independent rater. The MADRS at Weeks 8 and 10 may occur separately from the remote trial site visit but must be performed within the window.
- The C-SSRS will be administered by trial site staff.
- The GAD-7 will be completed by the subject.
- Concomitant medications and AEs will be recorded.

During each telephone contact by the trial site at Weeks 7 and 9, concomitant medications and AEs will be recorded.

All MADRS assessments during the trial will be conducted by the blinded and independent rater, and will be recorded. Regular quality reviews of MADRS audio recordings will be performed in order to verify the quality of the MADRS interview and accuracy of scoring. The process for data oversight will be outlined in the Site Operations Manual.

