Where $\Delta\mu$ WHODAS 2.0 CT-152+ADT and $\Delta\mu$ WHODAS 2.0 sham+ADT are the changes from baseline in Week 6 on the WHODAS 2.0 total score in CT-152+ADT and sham+ADT treatment groups, separately.

Change from screening to Weeks 4 and 6, separately, on the PHQ-9 total score will be analyzed using the same method as in the primary analysis with a replacement of the interaction term of visit by screening PHQ-9 total score as a covariate. The hypothesis tested is the null hypothesis that the change from screening to each schedule week (Weeks 4 and 6) in the PHQ-9 total score using CT-152+ADT is equal to the change from screening to each schedule week (Weeks 4 and 6) in the PHQ-9 total score using the sham+ADT.

 H_0 : $\Delta \mu_{PHO-9\ CT-152+ADT} = \Delta \mu_{PHO-9\ sham+ADT}$

 $H_A\text{: }\Delta\mu\text{ }_{PHQ\text{--}9\text{ }CT\text{--}152\text{+}ADT} \neq \Delta\mu\text{ }_{PHQ\text{--}9\text{ }sham\text{+}ADT}$

Where $\Delta\mu_{PHQ-9\ CT-152+ADT}$ and $\Delta\mu_{PHQ-9\ sham+ADT}$ are the changes from screening to Weeks 4 and 6 in PHQ-9 total score in CT-152+ADT and sham+ADT treatment groups, separately.

Partial response on the MADRS is defined as \geq 30% and < 50% reduction in MADRS total score from baseline. Partial response rates at Weeks 2, 4, and 6, separately, will be analyzed using the same statistical model for MADRS response.

 H_0 : $\pi_{CT-152+ADT} = \pi_{sham+ADT}$

 H_A : $\pi_{CT-152+ADT} \neq \pi_{sham+ADT}$

[figure not shown]
Protocol No. 345-201-00002

Where $\pi_{\text{CT-152+ADT}}$ and $\pi_{\text{sham+ADT}}$ are the MADRS partial response rates at Weeks 2, 4, and 6 in CT-152+ADT and sham+ADT treatment groups, separately.

Response on the MADRS during the extension period is defined as full or partial, defined as $\geq 30\%$ reduction in MADRS total score from baseline. Response rates at Weeks 8 and 10, separately, will be analyzed using summary statistics in LOCF analysis.

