## 10.3.4 Patient Health Questinaire-9 (PHQ-9)

The PHQ-9 is a standardized, self-administered rating scale that assesses the severity of depressive symptoms. The scale consists of 9 items, representing the 9 criteria upon which the diagnosis of DSM-IV depressive disorders is based. Each item is rated from 0 (not at all) to 3 (nearly every day). The total score ranges from 0 to 27. A higher score on the PHQ-9 represents a higher severity of depressive symptoms. PHQ-9 is assessed at screening, and Weeks 4 and 6.

[figure not shown]

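### PHQ-9 has no Day 1 assessment, so its change and its covariate both rest on an older screening score; the arm comparison stays unbiased, but some precision may be lost

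*Protocol*

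**What the plan says.** The Synopsis and Table 3-1 of the protocol list "Change from screening to Weeks 4 and 6 in the PHQ-9 total score" among the other efficacy endpoints. Table 1.3-1 marks PHQ-9 at screening, Week 4 and Week 6, and SAP 10.3.4 agrees: "PHQ-9 is assessed at screening, and Weeks 4 and 6".

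The other visible efficacy scales all have a Day 1 entry in Table 1.3-1. For the baseline visit, Protocol Section 8 says of the self-reports "The following will be completed by the subject: GAD-7 and WHODAS 2.0" and of the site ratings "The following will be administered by the trial site staff: CGI-S and C-SSRS". For the primary scale it says "The baseline MADRS must be completed prior to or on the day of the baseline visit".

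Protocol 9.4.1.2.3 analyses PHQ-9 by the primary mixed model "with a replacement of the interaction term of visit by screening PHQ-9 total score as a covariate". Screening needs at least 7 consecutive days and is planned for up to 3 weeks, but the Synopsis adds: "Extensions to the screening period, if requested by the investigator, may be granted after discussion and approval by the medical monitor". No limit on an extension is given.

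SAP 8.3 tests the other efficacy endpoints at a nominal two-sided 0.05 without multiplicity adjustment. Section 2 of the SAP addendum keeps that rule for everything except the primary endpoint.

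**The concern.** The screening interval is not a quiet one. Washout of prohibited drugs starts after consent (Protocol Section 8), anxiolytics are tapered and stopped before Day -1 (6.5.1), and users of mental-health apps must stop them at screening (exclusion criterion 9). A change measured from screening therefore adds whatever happens in this interval, and any regression to the mean, to the change during treatment. The within-arm PHQ-9 change then does not cover the same period as the change on scales measured from baseline.

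The second issue is the covariate. A score that is 1 to 3 weeks older may predict Weeks 4 and 6 less well than a Day 1 score would, leaving more residual variance. PHQ-9 is the only self-rated depression scale in the visible text, no visible eligibility criterion uses it, and no visible reason is given for leaving it out on Day 1.

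**Working it through.** **The plan's own figure.** The documents size only the MADRS endpoint: difference 3, SD 9, two-sided 0.05, power 85% (Protocol 9.1). Per arm, n = 2 × 9² × (1.960 + 1.036)² / 3² = 161.6, so 162 per arm and 324 in total; 324 / 0.90 = 360 randomized. This reproduces the plan, but it gives no PHQ-9 SD, effect, correlation or power.

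**How much of the change precedes randomization.** This assumes that PHQ-9 is completed around the screening visit, 7 to 21 days before Day 1.
- Week 6: 7 / (42 + 7) = 14% to 21 / (42 + 21) = 33% of the interval.
- Week 4: 7 / (28 + 7) = 20% to 21 / (28 + 21) = 43%.

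**Is the arm comparison affected?** Write Y for the Week 6 score, S for the screening score and T for treatment. The model Y − S = a + τT + bS is the same as Y = a + τT + (b + 1)S. The treatment effect τ is identical for the change and for the raw score. Because the plan fits a slope for S at each visit, this holds at Week 4 too. S precedes randomization in both arms, so drift enters only the within-arm means.

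**Precision.** Residual variance after adjustment is proportional to 1 − ρ². The variance ratio, screening covariate against Day 1 covariate, is (1 − ρ_scr²) / (1 − ρ_day1²). All correlations below are assumptions.

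| ρ_day1 | Screening keeps 95% | Screening keeps 80% |
|---|---|---|
| 0.3 | 0.9188 / 0.91 = 1.010 | 0.9424 / 0.91 = 1.036 |
| 0.5 | 0.7744 / 0.75 = 1.032 | 0.84 / 0.75 = 1.120 |
| 0.7 | 0.5578 / 0.51 = 1.094 | 0.6864 / 0.51 = 1.346 |

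If the two correlations are equal, the ratio is 1 and nothing is lost.

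To give the middle row a scale, suppose an endpoint would have 85% power with Day 1 adjustment. Power with the screening covariate is Φ(2.996 / √ratio − 1.960).
- With 90% kept (ρ_scr 0.45), the ratio is 0.7975 / 0.75 = 1.063, the standard error rises 3.1%, 324 subjects are worth about 305, and power is 82.8%.
- With 80% kept (ρ_scr 0.40), the standard error rises 5.8%, 324 are worth about 289, and power is 80.8%.

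**What baseline MADRS could recover.** With two covariates, R² = (r₁² + r₂² − 2r₁r₂r₁₂) / (1 − r₁₂²). Here r₁ is screening PHQ-9 with outcome, r₂ is baseline MADRS with outcome, and r₁₂ = 0.5 is the assumed correlation between the covariates. The reduction in residual variance is 1 − (1 − R²) / (1 − r₁²).

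| r₁ | r₂ = 0.3 | r₂ = 0.4 |
|---|---|---|
| 0.3 | R² 0.120, cut 3.3% | R² 0.173, cut 9.2% |
| 0.4 | R² 0.173, cut 1.6% | R² 0.213, cut 6.3% |
| 0.5 | R² 0.253, cut 0.4% | R² 0.280, cut 4.0% |

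The range is about 0.4% to 9%.

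**The case against.** The strongest reply is that this is an open and consistent design choice. The endpoint is defined from screening wherever it appears, the protocol's covariate matches it, and the comparison of arms is valid. That stands: there is no contradiction to reconcile.

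The stakes are also low. PHQ-9 has no power target and no error control, and the visible list of endpoints supporting the primary result in Section 3 of the SAP addendum contains only MADRS measures. That stands too.

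The precision loss is assumed, not shown. This is correct, and is why zero belongs at the lower end of the range.

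Other points narrow the argument about drift:
- HAM-D17 of at least 18 is required at both screening and Day 1, which limits randomization of subjects who improve during screening. Because Day 1 is itself a selection point, a Day 1 PHQ-9 would not be free of regression to the mean.
- The onboarding sessions are stated to carry no therapeutic content, so they are weak evidence of drift.
- A reader might take the MADRS change to start strictly on Day 1. Baseline MADRS may be done earlier, and no earliest date is given.

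Finally, some efficacy rows of Table 1.3-1 are redacted, and SAP 7.5 shows a redacted measure also summarised at screening. The statement that PHQ-9 stands alone applies to visible scales only, and a reason for the timing may lie in text that is not shown.

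None of this explains why a short self-report is omitted at a visit where two others are completed.

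**Conclusion.** The point holds as a minor design weakness. PHQ-9 is the only visible efficacy scale without a Day 1 value, and both its change and its model covariate rest on a score about 7 to 21 days old at randomization, or older after an extension.

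The consequences are a possible loss of precision and within-arm changes that include pre-randomization drift. Under the stated assumptions the extra variance is zero when both scores predict equally well. It is about 1% to 4% at a Day 1 correlation of 0.3, 3% to 12% at 0.5, and 9% to 35% at 0.7.

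A reader might infer that the PHQ-9 treatment effect is biased, or that a material loss of power is established. The documents support neither: the algebra rules out the first, and no PHQ-9 correlation is given from which to show the second. The primary MADRS result is not touched.

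**What to change.** **If the protocol can be amended before enrolment:** add PHQ-9 to the Day 1 self-reports in Table 1.3-1 and Protocol Section 8, completed before first use of the app. Define the endpoint as change from Day 1, with Day 1 PHQ-9 by visit as the covariate. The cost is one extra 9-item electronic form.

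**If subjects are already randomized:** keep change from screening for everyone. Switching later subjects to Day 1 would mix two reference points in one endpoint. Before unblinding, prespecify baseline MADRS by visit as an additional covariate in the PHQ-9 mixed model, alongside screening PHQ-9 by visit. Describe it as the baseline value, since it may precede the Day 1 visit. This costs SAP wording only. It drops nobody from the full analysis set, whose definition already requires a baseline MADRS. The expected gain is about 0.4% to 9% of residual variance under the correlations assumed above, so it may be small.

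In either case, SAP 8.3 should name the PHQ-9 covariate, which at present only Protocol 9.4.1.2.3 does. If change from screening is kept, tables of within-arm PHQ-9 change should carry a note that the interval starts before randomization.
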